The study population will include pregnant women between the ages 18 and 45 years enrolled as cases and controls. Women at high risk for preeclampsia will be enrolled as cases and those without risk factors for preeclampsia will be approached to serve as a control population. Approximately 250 eligible women will be enrolled in this study (50 in the normal control arm, 100 in the low dose 81 mg per day arm, and 100 in the 162 mg per day arm). Eligible patients will be recruited from UK clinics and the UK Good Samaritan ultrasound unit at the time of their scheduled prenatal visits or ultrasound appointments. Women who plan to deliver at University of Kentucky Chandler Hospital will be approached for enrollment.

The risk factor assessment to screen women at high risk for preeclampsia include:

1. History of preterm preeclampsia, especially when accompanied by an adverse outcome
2. Chronic hypertension
3. Type 1 and Type 2 diabetes
4. Renal diseases
5. Autoimmune disease

Exclusion criteria include:

1. Pregnant women younger than 18 years or older than 45 years
2. Multiple gestations
3. History of allergy (urticaria or anaphylaxis) to aspirin or aspirin related products asthma that worsens after aspirin use
4. Patients with gastrointestinal or genitourinary bleeding
5. Patients with peptic ulcer disease
6. Patients with severe liver dysfunction
7. Patients who have undergone bypass surgery
8. Patients on anticoagulant medication(s)
9. Women with anomalous fetus

Recruitment and data collection is expected to last throughout 2018-2022 academic years. Data analysis is expected to be accomplished during 2019-2022 academic years.

Attachments

Indicate the targeted/planned enrollment of the following members of minority groups and their subpopulations. Possible demographic sources: [Census Regional Analyst Edition](#), [Kentucky Race/Ethnic Table](#), [Kentucky Population Data](#).

(Please note: The IRB will expect this information to be reported at Continuation Review time for Pre-2019 FDA-regulated Expedited review and Full review applications):

Participant Demographics

	Cisgender Man 	Cisgender Woman 	TGNB/TGE 	Unknown/Not Reported
American Indian/Alaskan Native:	0	2		
Asian:	0	10		
Black/African American:	0	35		
Latinx:	0	25		
Native Hawaiian/Pacific Islander:	0	2		
White:	0	166		
American Arab/Middle Eastern/North African:		1		
Indigenous People Around		1		

the World: _____

More than One Race:	8		
Unknown or Not Reported:	0	0	

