The facilities that will be used for the study will be UK Chandler hospital, UK Polk Dalton clinic, UK Good Samaritan hospital, UK Good Samaritan ultrasound unit, UK Good Samaritan Radiology unit and UK laboratories. The blood and urine samples will be de-identified and stored in [name] lab at the University of Kentucky. The participants will continue to receive prenatal care as per their standard prenatal care from their obstetricians. If any medical concerns are addressed they will be immediately be referred back to their obstetrician.

Potential Risks & Benefits

Risks

- Describe any potential risks – including physical, psychological, social, legal, ability to re-identify subjects, or other risks. Assess the seriousness and likelihood of each risk.
- Which risks may affect a subject's willingness to participate in the study?
- Describe likely adverse effects of drugs, biologics, devices or procedures participants may encounter while in the study.
- *Qualitative research* - describe ethical issues that could arise while conducting research in the field and strategies you may use to handle those situations.
- Describe any steps to mitigate these risks.

Benefits

- Describe potential direct benefits to study participants – including diagnostic or therapeutic, physical, psychological or emotional, learning benefits. This cannot include incentives or payments.
- State if there are no direct benefits.
- Describe potential benefits to society and/or general knowledge to be gained.

Describe why potential benefits are reasonable in relation to potential risks. If applicable, justify why risks to vulnerable subjects are reasonable to potential benefits.

The most common side effects seen with aspirin use are but not limited to nausea, vomiting, heartburn in the mother seen in about 10% of the patients. There is no increased risk for bleeding during antepartum, intrapartum or postpartum period and there are no known fetal risks with low dose aspirin. There is no risk to the control group involving low risk pregnant women as they do not meet criteria to receive aspirin during the study or outside of it.

The ultrasound assessments of the uterine and brachial arteries are non-invasive and do not pose any maternal or fetal risks. Patients may experience discomfort using ultrasound assessment of the brachial artery which involves inflating the blood cuff around the forearm for 5 minutes.

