Women will be screened for any history of allergy to aspirin or aspirin related products, history of gastrointestinal or genitourinary bleeding, history of gastric bypass surgery, peptic ulcer disease or liver dysfunction prior to initiating aspirin to minimize undesirable side effects of aspirin. Patients on anticoagulant medication(s) will be excluded from this study. A data and safety monitoring plan will be implemented.

They can choose to leave the study at any time without any consequences to the standard prenatal care they would receive. Risk of breech of confidentiality - Patients' data will be de-identified and will be assigned a coded identification number. Women will be informed that their data will be stored in a locked cabinet behind a locked door or on a password protected computer behind a locked door in the PI's office located in the [name]. All possible safety measures will be initiated to protect patient information. Despite all this, should any breech occur, we will contact patients immediately and work with IRB to correct any problems

[UK IRB policies](#) state that IRB-related research records must be retained for a minimum of 6 years after study closure.
Check this item to confirm that you will retain all IRB-related records for a minimum of 6 years after study closure.

Payment

Describe the incentives (monetary or other) being offered to subjects for their participation. If monetary compensation is offered,

indicate the amount and describe the terms and schedule of payment. Please review [this guidance](#) for more information on payments to subjects, including restrictions and expectations.

The subjects will not be offered any incentives for their time during participation in the research study

Costs to Subjects

Include a list of services and/or tests that will not be paid for by the sponsor and/or the study (e.g., MRI, HIV). Keep in mind that a subject will not know what is "standard" – and thus not covered by the sponsor/study – unless you tell them.

Patients' insurance company, Medicare, or Medicaid will be responsible for the costs of all care and treatment that they would normally receive for any conditions they may have. These are costs that are considered medically necessary and will be part of the care they receive even if they do not take part in this study.

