The technique to measure flow mediated dilation has been validated and used extensively in research involving pregnant women. Patients may experience discomfort at the time of cuff inflation in their forearm for 5 minutes. We will continue to monitor patients during their hospitalizations and monitor for an increase between groups in adverse maternal and neonatal outcomes as defined as placental abruption, postpartum hemorrhage, epidural or spinal hematoma, fetal intracranial hemorrhages, premature closure of ductus or maternal deaths. PI will implement these monitoring procedures and data will be reviewed at 6- month intervals to determine if a significant increase in adverse events is noted between groups.

2. Assuring compliance with the requirements regarding the reporting of unanticipated problems or adverse experiences:

The PI will review the collected data at regular intervals to determine if adverse maternal or neonatal events are potentially related to the exposure. If a root cause analysis suggests that the adverse or unanticipated outcome is due to patient's participation in this research, then a severe adverse event will promptly be reported to IRB. The patient will also be notified and aspirin dosing will be changes as needed.

3. Any action resulting in a temporary or permanent suspension of the study is reported to the IRB promptly. This would include but not limited to a increase in serious maternal and neonatal adverse events as defined above

4. Assuring data accuracy and protocol compliance The PI will monitor data accuracy and protocol compliance

5. Assuring communication among multi-center sites adequately protects the participant (if this is a multi-center study in which the lead PI or UK is the coordinating institution) - Not applicable

[Back to Top](#)

Future Use and Sharing of Material (e.g., Data/Specimens/Information)

If the material collected for this study will be used by members of the research team or shared with other researchers for future studies, please address the following:

- list the biological specimens and/or information that will be kept
- briefly describe the types, categories and/or purposes of the future research
- describe any risks of the additional use
- describe privacy/confidentiality protections that will be put into place

- describe the period of time specimens/information may be used
- describe procedures for sharing specimens/information with secondary researchers

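### The defined between-group safety outcomes omit gastrointestinal intolerance, the one maternal aspirin side effect the protocol quantifies, and gastrointestinal or genitourinary bleeding, so neither has a described route into the 81 mg versus 162 mg comparison

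*Combined protocol and SAP*

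**What the plan says.** **What is compared.** Data and Safety Monitoring, item 1, reads "We will continue to monitor patients during their hospitalizations and monitor for an increase between groups in adverse maternal and neonatal outcomes", and defines those outcomes "as defined as placental abruption, postpartum hemorrhage, epidural or spinal hematoma, fetal intracranial hemorrhages, premature closure of ductus or maternal deaths". The investigator applies this on a fixed cycle: "data will be reviewed at 6- month intervals to determine if a significant increase in adverse events is noted between groups". Item 3 refers back to the same definition when it describes suspension of the study.

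**What is expected from aspirin.** Potential Risks & Benefits gives the most common effects as "nausea, vomiting, heartburn in the mother seen in about 10% of the patients". The figure is not split by dose. No other maternal side effect of aspirin is given a rate anywhere in the documents.

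**What is screened at entry.** The exclusion criteria list "Patients with gastrointestinal or genitourinary bleeding". Records, Privacy, and Confidentiality says women are screened for "history of gastrointestinal or genitourinary bleeding, history of gastric bypass surgery, peptic ulcer disease or liver dysfunction prior to initiating aspirin", with the stated purpose of limiting aspirin's side effects.

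**How long treatment runs.** Under Study Design, aspirin starts between 11 and 16 weeks and continues to 36 weeks. Women are seen at routine prenatal visits, with two study scans after enrolment.

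**What is analysed.** The Statistical Analysis Plan contains no safety analysis.

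**The concern.** The randomised contrast is one aspirin dose against twice that dose, and the stated objective is dose response. Potential Risks & Benefits suggests a possible greater benefit on 162 mg and says the findings may help tailor care by dose. If benefit is compared by dose but the side effect the protocol itself expects is not, readers get one side of the balance.

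The six defined outcomes are serious events. The only setting named for observing patients is a hospital admission, while the tablets are taken at home. Nausea, heartburn or minor bleeding that does not lead to admission has no described way into the six-monthly review or the final report. The trial could then report no difference in defined adverse outcomes without having counted the expected one.

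A lesser consequence is possible. Intolerance is a plausible reason for missed tablets, which would bear on how the pulsatility index and flow-mediated dilation contrasts are read. The documents do not make this link, so it is a reason to record the symptoms and not a demonstrated bias.

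**Working it through.** The plan states no safety rate difference, alpha or power, so it has no figure to reproduce. The check has two parts.

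**1. Is there another route for these events?**
- Item 1: six named outcomes, none gastrointestinal or genitourinary.
- Item 2: the investigator reviews the collected data for adverse maternal or neonatal events. This is broader than item 1, but it depends on what is collected.
- Research Procedures: chart abstraction names treatment course and neonatal complications, not maternal side effects.
- Records, Privacy, and Confidentiality: the research materials listed are demographics, chart abstraction, ultrasound, blood and urine. Symptom questions are not mentioned.
- Data collection sheet and procedures timeline: attached to the application but not shown, so their content is unknown.

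No visible text describes such a route.

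**2. What would counting them yield?**

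Inputs:
- 100 women per aspirin arm (enrolment text: 50 controls, 100 and 100).
- Project Information gives a maximum of 209. If 50 are controls (assumption), (209 − 50)/2 = 79.5, about 80 per arm.
- 10% taken as the 81 mg rate (assumption, because the protocol does not split by dose).
- Rates for 162 mg and two-sided alpha 0.05 are assumptions.

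Time on treatment: 36 − 16 = 20 weeks to 36 − 11 = 25 weeks.

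Expected count: 100 × 0.10 = 10 women per arm, or 80 × 0.10 = 8.

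95% interval for a difference (Wald): d ± 1.96 × √[p₁(1 − p₁)/n + p₂(1 − p₂)/n].
- 10% v 10%, n = 100: 1.96 × √(0.0009 + 0.0009) = 0.083, so ±8.3 points.
- 10% v 10%, n = 80: 1.96 × √(0.001125 + 0.001125) = 0.093, so ±9.3 points.
- Observed 20% v 10%, n = 100: 10 ± 1.96 × 5.0, so 0.2 to 19.8 points.
- Observed 20% v 10%, n = 80: 10 ± 1.96 × 5.59, so −1.0 to 21.0 points.

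Power (two-sided 0.05, 1:1; normal approximation / Fisher exact):

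| True rates | n = 100 | n = 80 |
|---|---|---|
| 10% v 15% | 19% / 14% | 16% / 11% |
| 10% v 20% | 51% / 44% | 42% / 35% |
| 10% v 25% | 80% / 76% | 71% / 65% |
| 10% v 30% | 95% / 94% | 89% / 87% |

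By the normal approximation, 80% power needs a rate of about 25% at 100 per arm, or about 27% at 80 per arm. To detect 20% v 10% with 80% power would take 199 per arm.

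For scale, the only rates given for an event close to a listed outcome are 0.1% and 0.3%, for neonatal intraventricular haemorrhage in a cited trial of 150 mg. At 100 per arm that is 0.1 to 0.3 expected events per arm. The chance of even one event among 200 women is 1 − 0.999²⁰⁰ = 18% to 1 − 0.997²⁰⁰ = 45%.

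No rate is given for gastrointestinal or genitourinary bleeding, so no count can be worked out for it.

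**The case against.** The strongest reply is that this is a mechanistic trial with no tolerability objective, and that a list of serious events is a defensible basis for deciding on suspension. That is fair as regards suspension. It does not explain why a randomised dose comparison should leave uncounted the one side effect the protocol quantifies.

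The reply also warns against four stronger readings, and on each it is right.

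- A reader might infer that gastrointestinal intolerance is the only harm frequent enough to compare. The documents give no rate for abruption or postpartum haemorrhage, both on the list, so this cannot be shown.
- A reader might extend the 10% to bleeding. It covers nausea, vomiting and heartburn only. Bleeding appears as an exclusion and a screened history, and the risk section says "There is no increased risk for bleeding during antepartum, intrapartum or postpartum period".
- A reader might conclude that such events could never reach the review. Item 2 is broader than the list, item 3 is expressly not exhaustive, and the data sheet is not shown. Confining all surveillance to admissions is also only one reading of item 1; the reference to hospital stays may attach only to its first clause.
- A reader might take the 0.2 to 19.8 interval as proof that the trial would detect a doubling. It describes an observed split of 20 against 10 in 100 each, for which Fisher's exact test gives p = 0.073 and uncorrected chi-square p = 0.048. If the true rates were 20% and 10%, power would be about 44% to 51%.

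Self-reported symptoms in an open-label trial are open to reporting bias. This stands, and it limits how the result should be labelled.

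**Conclusion.** The concern holds in a limited form. The defined between-group outcomes omit gastrointestinal intolerance, which the protocol expects in about 10% of patients, and gastrointestinal or genitourinary bleeding, which it screens for. Neither has a described route into the 81 mg versus 162 mg comparison over 20 to 25 weeks of outpatient treatment.

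What is lost is a descriptive estimate: the difference in intolerance to within about ±8.3 points at 100 per arm, or ±9.3 at about 80, if both rates are 10%. A powered test is not lost, because the trial is too small for one unless the rate on one dose is roughly 2.5 times that on the other. These sizes rest on 10% as the 81 mg rate and, for the smaller case, on 50 of the 209 being controls. Nothing numerical can be said for bleeding.

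The improvement is worth making because it is cheap and changes what the dose comparison can report. If the data sheet already carries these items, what remains is to name them in item 1 and in the analysis.

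**What to change.** 1. In Data and Safety Monitoring, item 1, add gastrointestinal intolerance (nausea, vomiting, heartburn) because the protocol expects it. Add maternal gastrointestinal or genitourinary bleeding as a separate item because the protocol screens for it.
2. Ask the same fixed questions in all groups at the second and third study scans, alongside the hospital records. The second scan's window is given as 18 to 22 weeks in Study Design and 20 to 22 weeks in Research Procedures, so define the time point by scan number until these are reconciled. By the nominal windows, the third scan leaves the last 4 to 8 weeks of treatment (36 − 32 to 36 − 28), for which records must serve.
3. Tabulate both items by arm in the six-monthly review and the final report, as counts and rates with 95% intervals for the 81 mg versus 162 mg difference. State that this is descriptive, and which enrolment figure (250 or 209) applies.
4. Label the symptom item as self-reported in an open-label trial.

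The cost is a few questions at visits that already take place and more minor events to tabulate. No dosing or clinical management rule changes.

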Evidence for effectiveness of 162 mg vs. 81 mg of aspirin to reduce neonatal complications including intraventricular hemorrhage (IVH): The rate of IVH, necrotizing enterocolitis (NEC), respiratory distress syndrome (RDS), bronchopulmonary dysplasia (BPD), retinopathy of prematurity (ROP) and neonatal mortality are all dependent upon the gestational age and delivery and a reduction in early preterm birth will reduce the frequency of these adverse events.

a. Meta-analysis has documented exposure to low dose aspirin reduced the rate of preterm birth in indicated population (PARIS Collaboration trial)

b. Aspirin confers a greater benefit in the reduction of preterm preeclampsia at a dose of = 100 mg when initiated < 16 weeks of gestation (Roberge et al., 2018)

Low dose aspirin is defined as dosages between 50 mg and 325 mg of aspirin. The dose of 162 mg, which we intend to use in our study for preeclampsia prophylaxis, lies in the low dose range (Berger et al., 2008). Systematic reviews of randomized control trials of use of low dose aspirin in pregnancy have not demonstrated any maternal or fetal risks. ASPRE trial showed no difference in the rates of intraventricular hemorrhage (IVH) when pregnant women identified as high risk for preeclampsia received 150 mg of aspirin compared to those who received placebo (0.3% vs. 0.1%; OR 2.23, 95% CI: 0.09 -52.70). No significant differences were noted in other neonatal morbidities like anemia requiring blood transfusion and necrotizing enterocolitis between the aspirin and the placebo groups. With altered pharmacokinetics of aspirin in pregnancy, there is no physiological basis to believe a 12 mg increment in aspirin dose to 162 mg in our study poses a significantly increased risk for neonatal intraventricular hemorrhage.

In fact, a study currently underway at the University of Kentucky involves the use of Indomethacin, which is a stronger NSAID than aspirin in the prophylaxis of neonatal IVH in preterm infants. Several trials with 162 mg of aspirin in pregnancy for preeclampsia prophylaxis are currently registered in clinicaltrials.gov. Other institutions in United States and other countries have approved this dose for testing given the safety findings above as no fetal risks have been

identified.

D. Explain why any risk is the least possible for achieving the objectives of the research:

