Preeclampsia is a part of the spectrum of hypertensive disorders of pregnancy and is the leading cause of significant maternal and fetal morbidity and mortality. The incidence ranges from 3% to 8% of all pregnancies. The pathophysiology can involve multiple organ systems and the etiology is multi-factorial. Defective placental implantation, endothelial dysfunction, defective placental angiogenesis, platelet activation, oxidative stress and autoimmunity are some aberrant physiologies that contribute to preeclampsia. The potential role of endothelial dysfunction in the pathogenesis of disease was initially described in the pathogenesis of atherosclerosis and as a risk marker for cardiovascular events in non-pregnant adults. Ludmer et al demonstrated a paradoxical vasoconstriction with intracoronary infusion of acetyl choline in coronary atherosclerosis. This sentinel study led to an appreciation of a possible defect in endothelial vasodilation in human atherosclerosis. Furchtgott and Zawadski demonstrated the vascular endometrium released a substance named endothelial-derived relaxing factor (EDRF) which had the ability to influence the action of the underlying smooth muscle in the vascular wall. This substance was later identified as nitric oxide (NO). The existence of a nitric oxide dependent pathway, L-arginine-NO-CGMP pathway in pregnancy has been demonstrated in animal models (Weiner et al.). Yallampalli et al. examined the human endometrium at various gestational ages and demonstrated that the L-arginine-NO-cGMP pathway helped regulate myometrial contractility throughout gestation. Normal pregnancy is associated with profound cardiovascular changes with increase in cardiac output and heart rate and decrease in peripheral vascular resistance and mean arterial blood pressure. While endothelium-derived prostacyclin has shown to have a role, nitric oxide has been identified as an important regulator of blood pressure in pregnancy. Molnar and Hertelendy used animal models to show prolonged blockade of nitric oxide synthase inhibitor leads to a preeclampsia like state with sustained hypertension, thrombocytopenia, a reduced intravascular compartment, fetal growth retardation and potentially fetal demise. Additional evidence of endothelial dysfunction in preeclampsia in humans was provided by McCarthy et al. Small arteries from the subcutaneous fat were examined at the time of cesarean section in normal pregnant women and women with preeclampsia. The authors showed acetylcholine(endothelial) mediated relaxation of the arteries was impaired in women with preeclampsia compared to normotensive pregnant women providing evidence of endothelial dysfunction in preeclampsia.

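### The adverse outcomes compared between groups include maternal death but not miscarriage, stillbirth or neonatal death

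*Combined protocol and SAP*

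**What the plan says.** The monitoring plan is in the protocol's Data and Safety Monitoring section. Three of its items matter here.

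- **Item 1** sets the comparison between groups. The investigator will "monitor for an increase between groups in adverse maternal and neonatal outcomes as defined as placental abruption", and the definition continues to the end of the list: "placental abruption, postpartum hemorrhage, epidural or spinal hematoma, fetal intracranial hemorrhages, premature closure of ductus or maternal deaths". That is six outcomes. The trigger is that "data will be reviewed at 6- month intervals to determine if a significant increase in adverse events is noted between groups". No test, threshold or denominator is given.
- **Item 2** is a review of causality: "The PI will review the collected data at regular intervals to determine if adverse maternal or neonatal events are potentially related to the exposure". It is not restricted to the item 1 list. Prompt reporting to the IRB follows if a root cause analysis attributes the outcome to taking part.
- **Item 3** concerns reporting a suspension of the study to the IRB: "This would include but not limited to a increase in serious maternal and neonatal adverse events as defined above".

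Elsewhere, part C of the section on research involving pregnant women or fetuses gives a series of neonatal complications that ends "retinopathy of prematurity (ROP) and neonatal mortality are all dependent upon the gestational age", and argues that fewer early preterm births would make these adverse events less frequent. Research Procedures says that delivery and neonatal information, including neonatal complications, will be abstracted from medical records. The short SAP describes no safety analysis.

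**The concern.** Item 1 is the only place where the plan commits to comparing harms between groups, and it does so through a definition. An outcome outside the definition is outside the planned comparison. Death of the mother is in; death of the fetus or newborn is out. The trial compares two doses in pregnancies selected for high risk, and the protocol itself places neonatal mortality among the adverse events that matter.

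The arm comparison matters because a single loss in a high-risk pregnancy can seldom be attributed to a dose. An excess on one arm would show mainly in counts set side by side. The trial is also open-label and the investigator conducts the review, so a list fixed in advance carries more weight.

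A lesser problem concerns the two fetal events that are listed. If nobody records how many fetuses or infants were assessed for them, a row of zeros may be read as evidence of safety when it is not.

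**Working it through.** The plan states no safety sample size, error rate or boundary, so there is no figure to reproduce.

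**1. Coverage of each item**

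| Outcome | Item 1: compared between groups | Item 2: relatedness review | Item 3: suspension |
|---|---|---|---|
| Maternal death | Named | Covered (maternal) | Covered |
| Neonatal death | Not named | Covered in general terms (neonatal) | Not named; wording open-ended |
| Miscarriage, stillbirth | Not named | Not named (only maternal or neonatal) | Not named; wording open-ended |

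Only the first column is a comparison by arm. Item 3's single example refers back to the item 1 list. Fetal loss is named nowhere in the three items.

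**2. What adding deaths would and would not give**

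Inputs: 100 women in each aspirin arm (protocol, study population section). Assumption: a two-sided Fisher exact test at 0.05, since the plan names no test.

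With 0 deaths in one arm and k in the other, p = 2 × C(100,k) / C(200,k).

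- k = 5: 2 × (100·99·98·97·96)/(200·199·198·197·196) = 2 × 0.0297 = 0.059
- k = 6: 2 × 0.0297 × (95/195) = 0.029

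Six deaths against none are needed. The protocol also gives a maximum of 209 subjects against about 250 planned. If that cap were shared in proportion, each aspirin arm would have about 209 × 100/250 = 84 women. The result is the same: k = 5 gives 0.059 and k = 6 gives 0.028.

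The documents give no loss rate. For illustration, an assumed 1% to 3% would mean 200 × 0.01 = 2 to 200 × 0.03 = 6 deaths among 200 randomised women. The chance that a tripling of the rate reaches Fisher p ≤ 0.05 is the sum of Bin(a; 100, p1) × Bin(b; 100, p2) over all significant outcomes with b > a:

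- 1% against 3%: 3%
- 2% against 6%: 17%
- 3% against 9%: 33%

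**3. Reading a zero count for the two listed fetal events**

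The one-sided 95% upper limit with 0 events in n assessed is 1 − 0.05^(1/n). The values of n are assumptions.

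- n = 100: 3.0%
- n = 50: 5.8%
- n = 10: 25.9%

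Even with all 100 assessed, zero is the likely result at the intraventricular haemorrhage rates that the protocol quotes from an earlier placebo-controlled trial of 150 mg (0.3% aspirin, 0.1% placebo): 0.997^100 = 74% and 0.999^100 = 90%.

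**The case against.** The strongest reply is that deaths would not go unnoticed. Item 2 covers adverse neonatal events without limiting them to the list, item 3 is expressly not limited to listed events, and neonatal complications are abstracted from records. The data collection sheet and the procedures timeline are attachments that are not reproduced, so fields for death may exist there. All of this stands. A reader might infer that an excess of perinatal deaths could pass with no review, or that deaths go unrecorded; the documents do not support either. What remains is that none of these provisions is a comparison by arm, and that items 2 and 3 speak of maternal and neonatal events, never fetal ones.

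A second reply is that adding deaths achieves little, because a significance trigger at this size will rarely fire. The calculation confirms this. It limits what the change can promise, but it is no reason to leave deaths out of the table.

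Three further inferences should be resisted.

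- The plan does not count the two fetal events over all women. It gives no denominator at all.
- Nothing shows that only a handful of babies per arm would be imaged. Routine fetal anatomy and growth scans are planned in every group, though the text does not say that they look for these events. That the events can be found only by imaging is clinical inference.
- The background phrase "fetal growth retardation and potentially fetal demise" describes animal models of nitric oxide synthase blockade. It does not make fetal demise a named outcome of this trial.

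**Conclusion.** The point holds in a limited form. The list that defines the between-group safety comparison omits miscarriage, stillbirth and neonatal death while including maternal death, and items 2 and 3 do not supply the missing comparison. Fetal loss is the clearer gap because none of the three items names it; a neonatal death has at least the relatedness review.

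The size is modest. The change gives visibility of deaths by arm, not a test with useful power. The Fisher figures assume a two-sided 0.05 level and about 100 per arm, and the loss rates are illustrative.

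The denominator point is secondary. It is missing detail rather than a wrong rule, and its upper limits depend entirely on assumed numbers assessed.

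**What to change.** In item 1 of Data and Safety Monitoring, add to the defined outcomes: miscarriage or stillbirth after randomisation, and neonatal death before discharge. For the non-randomised control group, count from enrolment. Tabulate these by arm at each six-month review. Because item 3 refers back to the list, it then covers them without further change. State that the table is for inspection by arm and is not a powered test.

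For fetal intracranial haemorrhage and premature ductal closure, report three numbers by arm: events, fetuses or infants assessed, and infants born. No additional imaging or visit is needed.

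The cost is a few words in the protocol, a slightly longer six-monthly table, a count of those assessed and possibly one extra field for early losses, which delivery records may miss. Most of the rest should come from the delivery and neonatal records already being abstracted.
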